## 6.2 Preparation, Handling, Storage, and Accountability

The study intervention should be allowed to reach room temperature before use. It must be shaken before use. Prior to administration, the study intervention must be inspected visually for cracks, broken seals, correct label content, and extraneous particulate matter and / or discoloration, whenever solution and container permit. If any of these conditions exists, the study intervention must not be administered. Another dose is to be used, and the event is to be reported to the Sponsor.

The study intervention is to be administered intramuscularly into the deltoid muscle (preferably on the opposite arm from which blood was drawn before vaccination).

Participants must be kept under observation for 30 minutes after vaccination to ensure their safety, and any reactions during this period will be documented in the CRF.

- 1) The investigator or designee must confirm appropriate temperature conditions have been maintained during transit for all study intervention received and any discrepancies are reported and resolved before use of the study intervention.
- 2) Only participants enrolled in the study may receive study intervention and only authorized site staff may supply or administer study intervention. All study intervention must be stored in a secure, environmentally controlled, and monitored (manual or automated) area in accordance with the labeled storage conditions with access limited to the investigator and authorized site staff.
- 3) The investigator, institution, or the head of the medical institution (where applicable) is responsible for study intervention accountability, reconciliation, and record maintenance (ie, receipt, reconciliation, and final disposition records).
- 4) Further guidance and information for the final disposition of unused study interventions will be provided to the study personnel.

## 6.3 Measures to Minimize Bias: Randomization and Blinding

### 6.3.1 Randomization and Allocation Procedures

Randomization of participants will be performed with the blocked method, with stratification by age stratum. Each participant who meets all the inclusion criteria and none of the exclusion criteria and signs the ICF will be randomly assigned according to the participant's age group, to either Group 1, Group 2, or Group 3 via an interactive response technology (IRT) system, according to a 3:3:1 ratio.

Before vaccination, authorized qualified study staff will connect to the IRT system, enter the identification and security information, and confirm a minimal amount of data in response to IRT system prompts. The IRT system will then provide the vaccine dose identification number. Participant numbers and vaccine dose identification numbers will be recorded in the eCRF.

The full detailed procedures for group allocation are described in the IRT User Guide. If the participant is not eligible to participate in the study, then the information will only be recorded on the participant recruitment log.

If the dose initially allocated for vaccination cannot be used (eg, because the syringe broke or particulate matter was observed), authorized qualified study staff will obtain a replacement dose. Thus, the site personnel must contact the IRT system to receive the replacement dose allocation.

Participant numbers that are assigned by the IRT will consist of a 12-digit string (a 3-digit country identifier, a 4-digit study center identifier, and a 5-digit participant identifier). For example,

Participant 840000100005 is the fifth participant enrolled in Center Number 1 in the US (840 being the US country code).

Participant numbers should not be reassigned for any reason. The randomization codes will be kept securely in the IRT and an internal system.

### 6.3.2 Blinding and Code-breaking Procedures

The study will be conducted in a modified double-blind fashion:

- Investigators and study staff who conduct the safety assessment, laboratory personnel who analyze the blood samples, Sponsor's personnel and study Team members, and the participant will not know which study intervention is administered
- Only the study staff who prepare and administer the study intervention and are not involved with the safety evaluation will know which study intervention is administered

The investigator responsible for safety assessment will not attend the vaccination session but will be available in case of emergency (eg, anaphylactic shock).

Dose numbers will be used to identify each vaccine vial for the purpose of randomization, vaccination, and the recording of vaccine dose administered. Dose numbers will be randomly assigned to the 3 study interventions. The IRT vendor will be responsible for providing the participant identification and dose number to be received by the enrolled participant.

The code may be broken in the event of an AE only when the identification of the study dose intervention received could influence the treatment of the participant. Code-breaking should be limited to the participant(s) experiencing the AE.

The blind can be broken by the investigator or a designee through the IRT system. Once the emergency has been addressed by the site, the investigator or a designee must notify the Sponsor's RMO if a participant's code was broken. All contact attempts with the Sponsor prior to unblinding are to be documented in the source documents, and the code-breaking CRF is to be completed.

The Institutional Review Board (IRB)/Independent Ethics Committee (IEC) must be notified of the code-breaking, in accordance with local regulations. All documentation pertaining to the event must be retained in the site's study records and in the Sponsor's files. Any intentional or unintentional code-breaking must be reported, documented, and explained, and the name of the person who requested it must be provided to the Sponsor.

A request for the code to be broken may also be made:

- by the Global Pharmacovigilance (GPV) Department through an internal system for reporting to Health Authorities in the case of an unexpected SAE considered causally related, as described in International Council for Harmonisation (ICH) E2A. In this case, the code will be broken only for the participant(s) in question. The information resulting from code-breaking (ie, the participant's study intervention or group assignment) will not be communicated to either the investigator or the immediate team working on the study, except for the GPV representative.

At the time of the interim analysis (see [Section 9.5](#)), study unblinding will take place to inform selection of the dose formulation for Phase III clinical development. The unblinding code data will be maintained with the Sponsor until the end of the study. The study team will strive not to communicate the study unblinding data to sites in order to minimize bias in collecting the follow-up safety data. The study participants and the laboratory personnel who analyze the blood samples for the study will remain blinded throughout the study.

## 6.4 Study Intervention Compliance

The following measures will ensure that the study intervention is administered as planned (see [Table 6.1](#)), and that any non-compliance is documented so that it can be accounted for in the data analyses:

- All study interventions will be administered by qualified and trained study personnel
- The person in charge of study intervention management at the site will maintain accountability records of study intervention delivery to the study site, study intervention inventory at the site, dose(s) given to each participant, and unused or wasted doses

For a regional or national emergency declared by a governmental agency that results in travel restrictions, confinement, or restricted site access, contingency measures are included in [Appendix 10.5: Contingency Measures for a regional or national emergency that is declared by a governmental agency](#).

## 6.5 Dose Modification

Not applicable.

## 6.6 Continued Access to Study Intervention After the End of the Study

Not applicable.

## 6.7 Treatment of Overdose

Since the study intervention is administered by a health care professional, it is unlikely that overdose by injection occurs.

However, in the event of an overdose, the investigator should:

- 1) Contact the RMO immediately.
- 2) Evaluate the participant to determine, in consultation with the RMO, whether study intervention should be interrupted.
- 3) Closely monitor the participant for any AE/SAE.
- 4) Document the quantity of the excess of the overdose in the source documents.

## 6.8 Concomitant Therapy

At the time of enrollment, ongoing medications and other therapies (eg, blood products) should be recorded in the source document as well as new medications prescribed for new medical conditions / AEs during study participation.

Documentation in the CRF of ongoing concomitant medication(s) will be limited to specific categories of medications of interest beginning on the day of first vaccination.

Reportable medications include medications that may affect the interpretation of safety data (eg, an antipyretic or analgesic that could have reduced the intensity or frequency of an adverse event) or may interfere with the development or measurement of the immune response (eg, the use of immune-suppressors, immune-modulators, or some antibiotics that can affect certain bioassays). Some medications such as steroids can affect both the evaluation of the safety and the immune response to a vaccine.

This may include medications of interest that were started prior to the day of vaccination, and even stopped prior to enrollment if there is a reasonable possibility that they may have an impact on safety and / or immune assessment during study participation.

The following reportable medications are defined:

- Medications impacting or that may have an impact on the evaluation of the safety (eg, antipyretics, analgesics, and non-steroidal anti-inflammatory drugs, systemic steroids/corticosteroids)  
Note: Topical analgesics should NOT be applied at the injection site of study intervention; however, if they are applied inadvertently, they should be recorded.
- Medications impacting or that may have an impact on the immune response (eg, other vaccines, blood products, antibiotic classes that may interfere with bioassays used by the Sponsor's laboratory or other testing laboratories, systemic steroids/corticosteroids, immune-suppressors, immune-modulators with immunosuppressive properties, anti-proliferative drugs such as DNA synthesis inhibitors)
- Medications impacting or that may have an impact on both the safety and the immune response (eg, systemic steroids/corticosteroids)

Reportable medications will be collected in the CRF until the end of the solicited and unsolicited follow-up period.

Dosage and administration route, homeopathic medication, topical and inhaled steroids, as well as topical, ophthalmic, and ear treatments will not be recorded (except topical analgesics applied at the injection site of study intervention). However, in case of an SAE, all medications and supplements including homeopathic medications taken for the SAE should be reported in the SAE form.

Medications given in response to an AE will be captured in the “Action Taken” section of the AE CRF only. No details will be recorded in the concomitant medication Form of the CRF unless the medication(s) received belongs to the reportable medications list. Medications will be coded using the WHO Drug dictionary.

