## 1.2 Schedule of Activities (SoA)

**Table 2.1 - Schedule of activities**

**Phase I/II Study, 5 Visits, 2 Vaccinations, 5 Blood Samples, 13 Months' Duration Per Participant**

Visit/Contact	Collection of information in the CRF	Visit 1	Visit 2	Visit 3	Visit 4	Visit 5
Study timelines (days)		D01	21 days post V01 (D22)	21 days post V02 (D43)	6 months post V02 (D202)	12 months post V02 (D387)
Time windows (days)			[+7 D]	[+7 D]	[+14 D]	[+14 D]
Visit procedures:						
Informed consent	X	X				
Inclusion/exclusion criteria	X	X				
Collection of demographic data	X	X				
Urine pregnancy test (if applicable)		X	X			
Collection of Medical history	X Significant Medical History*	X				
Physical examination		X	X			
Temporary and definitive contraindications	X		X			
Pre-vaccination temperature		X	X			
Randomization	X	X				
Allocation of participant number	X	X				
Dose assignment by IRT		X	X			
Blood sampling (BL) [40 mL/visit]	X	BL0001 Pre-vac	BL0002 Pre-vac	BL0003	BL0004	BL0005
Vaccination (vac)	X	X	X			

Visit/Contact	Collection of information in the CRF	Visit 1	Visit 2	Visit 3	Visit 4	Visit 5
eDiary provided†		X				
eDiary reviewed‡			X	X	X	X
Collection of solicited injection site and systemic reactions	X	X	X	X		
Collection of unsolicited adverse events (AEs)	X	X	X	X		
Collection of concomitant medications	X Reportable concomitant medication	X	X	X		
Collection of medically attended AEs (MAAEs)	X	To be reported at any time during the study				
Collection of serious adverse events (SAEs), including AESIs	X	To be reported at any time during the study				
Collection of pregnancies	X	To be reported at any time during the study				
End of Study Intervention Phase§	X			X		
End of study**	X					X

AESI: adverse event of special interest; CRF: case report form; D: day; DC: diary card; IRT: interactive response technology; V: visit

\* Significant medical history is described in [Section 8.2.1](#) of the protocol

† Electronic diary application should be downloaded to the participant's electronic device (such as mobile phone or tablet).

‡ Electronic diary is the primary method for safety data collection. However, paper diary cards will also be available for use as a back-up solution in case of major breakdown of the app or as determined by the Sponsor's study clinical team.

§ In case of participant discontinuation at a visit, the entire visit will be completed.

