**Table 2.1 - Identified and Potential risks of clinical significance and risk management**

Identified and Potential Risk of Clinical Significance	Summary of Data/Rationale for Risk	Risk Management
Investigated Vaccines: Panblok H7 (7.5 µg) + MF59; Panblok H7 (15 µg) + MF59 Comparator Vaccine: Panblok H7 (45 µg) unadjuvanted		
Anaphylactic reactions	Monitor non- important identified risk. All vaccines have the potential to cause allergic reactions or anaphylaxis in individuals who may be sensitized to components of the vaccine. Refer to IB Section 4.3 for more information regarding the components of the vaccine.	Observation period of 30 minutes after vaccination for early detection and treatment. Addressed in IB (administration precautions, potential adverse events), defined AESI in the study.
Guillain-Barré syndrome	Important potential risk. Influenza vaccines have the potential to cause Guillain-Barré syndrome	Exclusion criterion E14 for those with personal or family history of Guillain-Barré syndrome. Participants enrolling in the study will be informed of the potential AEs in the informed consent form (ICF) and will be advised to contact the study center to if a serious health problem occurs. Listed as AESIs in the study.

Identified and Potential Risk of Clinical Significance	Summary of Data/Rationale for Risk	Risk Management
Injection site reactions and systemic reactions	
Monitor non-important identified risks. Injection site reactions such as redness, swelling, pain, bruising, and induration around the area where the vaccine was injected were observed. Systemic reactions such as headache, myalgia, arthralgia, fever, malaise, shivering, and fatigue were also observed.
 
Most reactions resolved within 1 or 2 days without treatment.
 
Additional information on adverse reactions can be found in Section 7.1 of the IB.
	
Participants enrolling in the study will be informed of the potential adverse reactions in the ICF and will be advised to contact the study center if a serious health problem occurs.

Study Procedures		

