### Prior/concomitant therapy

**E08:** Receipt of any vaccine in the 14 days preceding Visit 1 or planned receipt of any vaccine prior to Visit 3, except for seasonal flu vaccine, which may be received at least 2 weeks after Visit 2

b The components of study interventions are listed in [Section 6.1](#) of the protocol and in the Investigator's Brochure.

c Chronic illness may include, but is not limited to, cardiac disorders, renal disorders, auto-immune disorders, diabetes, psychiatric disorders, or chronic infection

**E09:** Previous vaccination against H7N9 with an investigational vaccine

**E10:** Receipt of immune globulins, blood or blood-derived products in the past 3 months

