#### 7.1.2 Definitive Contraindications

Participants will permanently discontinue (definitive discontinuation) study intervention for the reasons listed below. These participants must not receive any additional dose of study intervention but should continue to be followed for safety and will not have any further blood sample drawn. Additional unscheduled visits may be performed for safety reasons and information will be reported in the source documents.

Should a participant experience at least one of the conditions listed below, the investigator will discontinue vaccination:

- DCI01: Pregnancy, as indicated by a positive urine test (if applicable)
- DCI02: An anaphylactic or other significant allergic reaction to the previous dose of vaccine
- DCI03: SAE assessed as related to the study vaccine following the previous dose of vaccine, based on Investigator's judgment
- DCI04: Receipt of any immune globulins, blood, or blood-derived products between V01 and V02
- DCI05: Known or suspected congenital or acquired immunodeficiency; or receipt of immunosuppressive therapy, such as anti-cancer chemotherapy or radiation therapy, since the preceding visit; or long-term systemic corticosteroid therapy (prednisone or equivalent for more than 2 consecutive weeks since the preceding visit)
- DCI06: Thrombocytopenia or bleeding disorder, which may be a contraindication for IM vaccination, based on Investigator's judgment
- DCI07: Chronic illness that, in the opinion of the investigator, is at a stage where it might interfere with study conduct or completion
- DCI08: Development of any condition that in the opinion of the Investigator would pose a health risk to the subject or could interfere with the evaluation of the study intervention (including Guillain-Barré syndrome, hepatitis B, or hepatitis C)

In the event of a local or national immunization program with a SARS-CoV-2 or other vaccine, participants who receive these vaccines at any time during the study will not be withdrawn from the study.

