#### *Unsolicited Non-serious Adverse Events*

Unsolicited non-serious adverse events will be collected from the day of vaccination (DX) until 21 days after each vaccination (DX + 21 days).

The intensity grading scale for unsolicited non-serious adverse events is presented in [Appendix 10.3.5.1.2](#).

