#### *Adverse Events of Special Interest (AESIs)*

AESIs will be collected throughout the study.

See [Section 8.3.6](#) for the list of AESIs.

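### Other vaccines and immune-modifying drugs leave the CRF at about D43, so the D202/D387 persistence and late safety summaries cannot account for an intervening vaccine

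*Protocol*

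**What the plan says.** Protocol section 6.8 lists the medications to be entered in the CRF. One class is medications that may affect the immune response; its examples include other vaccines, blood products, systemic steroids and immunosuppressants. The section then closes the window: "Reportable medications will be collected in the CRF until the end of the solicited and unsolicited follow-up period". Section 8.3.1 ends collection of unsolicited non-serious events 21 days after each vaccination. In the protocol's Schedule of Activities the row "Collection of concomitant medications" is marked at Visits 1, 2 and 3 and is empty at Visits 4 and 5. The SAP's Table 1.2 has the same pattern.

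Other follow-up runs much longer. On AESIs, section 8.3.1 says "AESIs will be collected throughout the study". It says the same of MAAEs, and takes SAEs to 12 months after the last vaccination. HAI and NT titres at D202 and D387 appear among the primary endpoints, and Protocol 9.5 gives persistence of antibody as the purpose of the final analysis.

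The plan expects other vaccines during follow-up. Exclusion criterion E08 bars planned vaccines before Visit 3, "except for seasonal flu vaccine, which may be received at least 2 weeks after Visit 2", and sets no limit afterwards. Sections 7.1.1 and 7.1.2 deal with public vaccination campaigns, against SARS-CoV-2 or anything else, and provide that "participants who receive these vaccines at any time during the study will not be withdrawn from the study".

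**The concern.** The trial stops recording an exposure that it classes as able to affect the immune response, yet goes on measuring that response for almost a year. A titre at D202 or D387 is read as persistence of the response to the study vaccine. If some participants received another vaccine in between, the summary cannot show how many, in which arm, or whether their titres differ.

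The same holds for late safety events. The protocol's risk table states "Influenza vaccines have the potential to cause Guillain-Barré syndrome", and Guillain-Barré syndrome is an AESI followed to the end of the study. Seasonal influenza vaccine is allowed during follow-up. If a late case occurs, the tables will not show how many participants in each arm had a recent influenza vaccine.

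**Working it through.** **1. Reproduce the timeline.** From the Schedule of Activities: Visit 2 = 1 + 21 = D22; Visit 3 = 22 + 21 = D43; Visit 4 = 22 + 180 = D202; Visit 5 = 22 + 365 = D387. The span is 387 − 1 = 386 days, and 386 / 30.4375 = 12.7 months, which agrees with the stated duration of approximately 13 months.

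**2. Length of the gap.** CRF collection ends at D22 + 21 = D43. Then 387 − 43 = 344 days, and 344 / 387 = 88.9%.

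**3. With every visit window fully used.** Visit 2 at D29; Visit 3 at 29 + 21 + 7 = D57; Visit 5 at 29 + 365 + 14 = D408. Taking collection to run to Visit 3, the gap is 408 − 57 = 351 days, and 351 / 408 = 86.0%. The result hardly depends on visit timing.

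**4. What falls in the gap.** Two of the five blood samples (D202, D387), and essentially all of the MAAE reporting intervals D43–D202 and D203–D387 in Protocol 9.4.3. Seasonal influenza vaccine is allowed from 22 + 14 = D36, so about the first week of that permission (D36 to D43) is recorded and the rest is not.

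**5. Would another record catch a routine preventive vaccine at, say, D120?**
- Source documents (6.8): therapies ongoing at enrolment, and new medications prescribed for new conditions or AEs. A preventive vaccine is neither.
- SAE form (6.8): "all medications and supplements including homeopathic medications taken for the SAE should be reported in the SAE form". This is treatment of the event, not exposure before it.
- Action Taken field of the AE form (6.8): medication given in response to an AE.
- 12-month questionnaire (8.3.2): MAAEs, SAEs and AESIs. Vaccines are not mentioned.
- Opening note of section 6: vaccines given outside the protocol are reportable in the CRF, but the note refers to 6.8 and so does not clearly extend its cut-off.
- Causality assessment (10.3.3): concomitant therapy is considered, but only for someone who has an event.
- SAP 3.4.4.1: no imputation and no outlier search. There is no rule for intervening vaccines.

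**6. Possible scale.** The documents give no uptake figure, so this is an assumption. If 20% to 70% of the 630 evaluable participants received any vaccine after D43, that is 0.20 × 630 = 126 to 0.70 × 630 = 441 people, or 9 to about 32 of the 45 evaluable in one Group 3 age stratum. The effect on titre is also not given. If a vaccine multiplied titres by k in a fraction f of an arm, the arm's GMT would be multiplied by k^f: 1.00 if k = 1 (no effect), and up to 2^0.70 = 1.62 if k = 2 and f = 70%.

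**The case against.** Much of the case on the other side stands, and it limits the point.

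- *A reader might infer that nothing is recorded after D43.* That is not so. Steroids or immunosuppressants prescribed for a new illness go in the source document with no D43 limit, and treatment of an AE goes in the Action Taken field. The gap is in the structured CRF record, and it is clearest for preventive vaccines.
- *A reader might infer that late events cannot be attributed.* This goes too far. Section 10.3.3 requires alternative causes, including concomitant therapy and timing, to be considered and investigated. Section 8.3.6 captures AESIs as SAEs, and the sponsor also assesses causality for these. The eDiary has free-text areas and is reviewed at Visits 4 and 5. A competent review of one Guillain-Barré case should bring out a recent vaccine. What is missing is the count of exposed participants without an event.
- *A reader might infer that the per-protocol set is undermined.* Its exclusion for immune-affecting medication has no stated time limit, but there is a single PPAS anchored on D22 and D43 samples, and no visit-specific set is planned for D202 or D387. All variables are also analysed on the FAS.
- *A reader might infer that dose selection is at risk.* It uses data to 21 days after dose 2, within the recorded period. The planned between-group differences and GMT ratios are at D22 and D43 only.

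Randomisation should also balance later vaccination on average, and the documents give no evidence that such vaccines move H7 titres. Balance is only partial in the small arm: at an assumed 50% uptake, 1.96 × √(0.25/135 + 0.25/45) = 0.169, so chance differences of about ±17 percentage points are possible between arms of 135 and 45 and could not be checked. Nor does randomisation help a within-arm description of persistence.

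**Conclusion.** The mismatch of collection windows is established from the documents: 344 of 387 days (89%; 86% with all windows used) have no structured record of vaccines or immune-modifying drugs. The consequence is confined to descriptive results: D202/D387 persistence within each arm, and aggregate summaries of late MAAEs, SAEs and AESIs. How many participants are affected, and whether their titres change, depends on the assumed uptake and effect; an effect of zero on titres is possible. The gap does not make late events unattributable or affect the D22/D43 conclusions. This is a cheap improvement, worth making before Visit 4 data are collected because unrecorded exposure is hard to recover afterwards.

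**What to change.** **Protocol.** In section 6.8 and both Schedules of Activities, extend CRF collection to Visit 5 for one limited category: vaccines received (type and date), immune globulins or blood products, and systemic immunosuppressants or steroids. Ask at the existing Visits 4 and 5 and in the 12-month questionnaire. Analgesics and antipyretics can stop at D43 as now.

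**SAP.**
- Add any prior vaccine, and the interval to onset, to the AESI, SAE and MAAE listings. The SAP does not currently mention MAAEs, so that listing should be tied to Protocol 9.4.3.
- Tabulate vaccines received after D43 by arm and age stratum.
- Add a D202/D387 titre summary that excludes, or splits by, such exposures. It should supplement the planned summary, not replace it, because it conditions on a post-randomisation event. It would also shrink Group 3: at the assumed 20% to 70% uptake, a stratum of 45 falls to 36 down to about 14.

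**Cost.** One short CRF page at two existing visits, some recall error over six-month intervals, and a protocol amendment with its approvals. No new visits, staff or procedures.
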